8.1.4 Visit 5 – EOT

The patient can attend the EOT Visit earliest at Day 14. This includes minimum 96 hrs of wash-out before the inhibitor sampling at the EOT Visit.

If the patient is ready for having the EOT Visit at Day 14, Visit 4 and the EOT Visit may be joined and all assessments pertaining to Visit 4 and EOT Visit must be performed once.

Before the EOT Visit and re-entering the pathfinder™ 2 trial the patient should be judged by the Investigator to be ready to continue either the prophylactic or on-demand treatment as previously decided upon in the pathfinder™ 2 trial. If not, the Post-operative Period must be extended beyond Day 14 as judged by the Investigator.

After having the EOT Visit, patients will return to pathfinder™ 2, reentering the prophylactic or on-demand treatment arm as per their prior participation in the trial.

A wash-out period of minimum 96 hrs is necessary prior to FVIII inhibitor and N8-GP antibodies sampling at EOT.

If a patient is prematurely withdrawn from the trial the Investigator must ensure that the procedures for Visit 5 (EOT Visit) are undertaken, if possible. A withdrawal session must be completed in the IV/WRS. The primary reason (AE, noncompliance with protocol or other) for discontinuation must be specified in the eCRF. If a subject is discontinued due to an ongoing AE from pathfinder™ 2, the primary reason for discontinuation must be entered under ‘other’ in the end of trial form. Even if the subject is not able to attend the visit, trial drugs should be returned, the end of trial form must be completed, a withdrawal call and drug accountability must be performed in the IV/WRS and the affirmation statement in the case book must be electronically signed off. The patient has been withdrawn from trial treatment and treated according to Investigator’s discretion.

In case of withdrawal due to FVIII inhibitor development, the patient should be scheduled for an EOT Visit as soon as possible and within 1 week after a positive inhibitor test is confirmed via re-testing at central laboratory, preferably prior to initiation of treatment with another FVIII product.

At EOT Visit the following assessments will be performed and/or recorded in the eCRF:

- Withdrawal criteria, see Section [6.5](#)
- Concomitant medication, see Section [11](#)
- Adverse events, see Section [12.1](#)

- Bleeding episodes and/or eDiary review and rating severity of bleeding episodes, see Section [8.2.2](#) and [8.4.7](#)
- Evaluation of wound haematoma, see Section [8.2.1.4](#)
- ECG, see Section [8.3.2](#)
- Physical examination, see Section [8.3.3](#)
- Vital signs, see Section [8.3.4](#)
- Body measurements (weight only), see Section [8.3.5](#)
- Check date and time of last coagulation factor administration, see Section [8.4.4](#)
- HE assessments, see Section [8.4.5](#)

Blood sampling for local laboratory assessments:

- Haematology, see Section [8.3.7.3](#)

Blood sampling for central laboratory assessments:

- Biochemistry, see Section [8.3.8.2](#)
- Coagulation parameters, see Section [8.3.8.3](#)
- FVIII activity, see Section [8.3.8.4](#)
- FVIII inhibitors, see Section [8.3.6.1](#)
- N8-GP binding antibodies, see Section [8.3.6.2](#)

Trial material, training and reminders

- eDiary review and rating severity of bleeding episodes, see Section [8.2.2](#) and [8.4.7](#)
- Return eDiary
- Drug accountability for all trial products dispensed or any product returned from the previous visits, see Section [9.4](#) and [10](#)
- Make completion call in IV/WRS, see Section [10](#)
- Make withdrawal call in IV/WRS, see Section [10](#)
- Affirmation statement
- End of trial

8.1.5 Follow-up Visit (only for patients withdrawn due to development of FVIII inhibitors)

In case of withdrawal due to FVIII inhibitor development, the patient should be scheduled for an EOT Visit as soon as possible and within 1 week after a positive inhibitor test is confirmed via re-testing, preferably prior to initiation of treatment with another FVIII product. One month (4 weeks \pm 2 weeks) after the EOT Visit the patient should attend a FU Visit, please see Section [8.3.6](#). At each FU Visit, it will be evaluated if further FU Visits are required. The additional FU Visits will be arranged at intervals of 4 weeks \pm 2 week as long as clinically warranted up until 3 months after confirmation of the FVIII inhibitor.

A wash-out period of minimum 72 hrs is necessary prior to FVIII inhibitors sampling at FU Visit.

The following will be performed and/or recorded in the eCRF:

- Bleeding episodes since last visit
- Vital signs, see Section [8.3.4](#)

Blood sampling for central laboratory assessments:

- FVIII inhibitors, see Section [8.3.6.1](#)

Reminder

- Follow up on any AEs according to Section [12.1](#)
- End of trial
- Affirmation statement

8.1.6 Unscheduled Visits

It is possible to perform Unscheduled Visits during the trial. The Unscheduled Visit can be performed at any time after the enrolment to and until the EOT Visit as either a telephone contact or a site visit. Patients can attend an Unscheduled Visit due to a bleeding episode, suspicion of inhibitor development, any AE, sampling for laboratory test etc. If the patient has any concerns regarding surgery (no improvement/worsening), the patient should contact the Investigator/Surgeon.

Visits/contacts to the site for the purpose of non-trial related activities do not need to be reported at an Unscheduled visit.

The following can be performed/reported at an Unscheduled Visit:

- Withdrawal criteria, see Section [6.5](#)
- Concomitant medication, see Section [11](#)
- Adverse events since previous visit, see Section [12.1](#)
- eDiary review and rating severity of bleeding episodes, see Section [8.2.2](#) and [8.4.7](#)
- Bleeding episodes (including date, severity and location) and eDiary compliance review, see Section [8.2.2](#) and [8.4.7](#)
- ECG, see Section [8.3.2](#)
- Physical examination, see Section [8.3.3](#)
- Vital signs, see Section [8.3.4](#)
- Body measurements, see Section [8.3.5](#)
- Antibodies (FVIII inhibitors and N8-GP binding antibodies), see Section [8.3.6.1](#)
- N8-GP specific IgE, IgG and anti-HCP (Host Cell Proteins) antibodies (conditional test), see Section [8.3.6.3](#)
- FVIII activity, see Section [8.3.7.2](#) and [8.3.8.4](#)
- Haematology, see Section [8.3.7.3](#)

- Biochemistry, see Section [8.3.8.2](#)
- Coagulation parameters, see Section [8.3.8.3](#)
- Check date and time of last coagulation factor administration (N8-GP) prior to Unscheduled Visit, see Section [8.4.4](#)
- Administration of trial product, see Section [8.5.1](#)
- Home treatment/eDiary training, see Sections [8.5.4](#) and [8.4.7](#)
- Dispensing of N8-GP for site dosing/home treatment must be performed via IV/WRS, see Section [10](#)
- Drug accountability of N8-GP, see Section [9.4](#) and [10](#)
- IV/WRS call, see Section [10](#)

8.2 Assessments for Efficacy

8.2.1 Surgical Interventions

Surgical procedure and duration:

- Type of surgery (e.g. arthroscopy)
- Indication (e.g. haemarthrosis)
- Location of surgery (e.g. left knee joint)
- Elective or emergency surgery
- Duration of surgical procedure
 - Start of surgery: date and time of first incision (“knife to skin”)
 - Stop of surgery: date and time of skin closure (“last stitch”)
- Clinical narrative incl. description of any complication, anticipated blood loss before surgery and estimation of blood loss after surgery, re-operation etc
 - Summary of surgery (through day 0)
 - Summary of Post-operative Period (Day 1-6)
 - Summary of Post-operative Period (Day 7-14)

8.2.1.1 Clinical Evaluation of Haemostatic Response

After completion of surgery (defined as “last stitch”) (Day 0, Visit 2) a clinical evaluation of haemostatic response during surgery will be assessed by the Surgeon or Anaesthesiologist or Investigator using a 4-point scale based on experience as follows:

1. **Excellent:** Better than expected/predicted in this type of procedure
2. **Good:** As expected in this type of procedure
3. **Moderate:** Less than optimal for the type of procedure but haemostatic response maintained without change of treatment regimen
4. **None:** Bleeding due to inadequate therapeutic response with adequate dosing, change of regimen required.

Clinical evaluation of haemostatic response during the Post-operative Period, Days 1-6 and 7-14 will be assessed by the definitions described in section [8.2.2.2](#).

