NN7088-3776	pathfinder™ 1 (phase 1 trial)
NN7088-3859	pathfinder™ 2 (pivotal trial)
NN7088-3860	pathfinder™ 3 (surgery trial)
NN7088-3861	pathfinder™ 4 (extension trial)
NOAEL	No Observed Adverse Effect Level
PCV	packed cell volume
pd-aPCC	plasma derived activated Plasma Coagulation factor Concentrates
pd-PCC	plasma derived Plasma Coagulation factor Concentrates
PEG	polyethylene glycol
PK	pharmacokinetics
PRO	patient reported outcomes
PT	Prothrombin time
PTP	previously treated patients
RBC	red blood cells
rFVIIa	recombinant activated factor VII
rFVIII	recombinant factor VIII
RIA	radioimmunoassay
SAE	serious adverse event
SAS	Safety Analysis Set
TEAE	Treatment emergent AE
T _½	terminal half-life
TMM	trial materials manual
TVP	trial validation plan
U	Unit
WFH	World Federation of Haemophilia

1 Summary

This trial will provide information on the efficacy and safety profile of NNC 0129-0000-1003, hereafter referred to as N8-GP, when administered before, during and after major surgery, see Section [5.3.1](#) for definition.

Primary Objective

- To evaluate the haemostatic effect of N8-GP during surgical procedures in patients with haemophilia A

Primary Endpoint

- Haemostatic effect during surgery evaluated by the four-point scale, assessed by the Investigator/surgeon at the day of surgery
 - Four-point response scale: excellent, good, moderate or none

Secondary Objectives

- To evaluate the general safety including immunogenicity of N8-GP when used for prevention and treatment of bleeding throughout the surgical period
- To evaluate the haemostatic effect of N8-GP during the post-operative period
- To evaluate health economic resource use (hospitalisation days) due to surgery

Key Secondary Endpoints

- Average consumption of N8-GP during surgery
- Haemostatic effect of N8-GP during the post-operative period Days 1-6 and 7-14
- Average consumption of N8-GP during the post-operative period Days 1-6
- Incidence rate of inhibitors against factor VIII (FVIII) (≥ 0.6 BU/mL)

The endpoints will be analysed based on all available information until End of Trial (EOT) Visit and up to approximately 5 weeks for each patient.

Trial design

The trial is a multi-centre, multi-national, open-label, non-randomised, single arm, efficacy and safety trial evaluating N8-GP during surgical procedures in patients with severe (FVIII activity (FVIII:C) <1%) haemophilia A.

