Patients undergoing surgery will receive bleeding preventive treatment with N8-GP before, during and after surgery. N8-GP doses will be adjusted based on the FVIII activity levels measured in the individual patient, see Section [5.4](#).

2 Flow Chart

Table 2–1 Visit Flow Chart

Visit number	1	2	3	4	5	Follow-up Visit FU ⁴	Un- scheduled Visit
Time of visit (Day)	Screening ¹	0 Surgery	1-6 ²	7-14 ²	EOT ³		
Visit window	0-3 w before Visit 2					4 w after EOT ±2 w	
SUBJECT RELATED INFO/ASSESSMENTS							
Informed consent	x						
In/exclusion criteria	x	x ⁵					
Withdrawal criteria		x ⁵	x	x	x		x
Bleeding treatment history	x ⁶						
Concomitant illness	x						
Concomitant medication	x	x	x	x	x		x
Infusions (concom. med.)		x	x	x			
Demography	x ⁶						
Genotype (FVIII genotype)	x ⁶						
Haemophilia details	x ⁶						
History of bleeding episodes	x ⁶						
History of surgery	x ⁶						
Medical history	x ⁶						
Date and time of last coagulation factor administration	x	x			x		x
EFFICACY							
Surgical interventions		x	x	x			
Clinical evaluation of haemostatic response		x	x	x			
Consumption of N8-GP		x	x	x			
Blood product transfusions		x	x	x			
Evaluation of wound haematoma		x	x	x	x		
Drain volume		x	x	x			
Haemoglobin		x	x	x			
Bleeding episodes		x	x	x	x	x	x
SAFETY							
Adverse events	x	x	x	x	x	x	x
ECG	x				x		x
Physical examination	x	x ⁵	x ⁷	x ⁸	x		x
Vital signs	x	x	x ⁷	x	x	x	x
Body measurements	x	x ^{5,9}	x ^{7,9}	x ⁹	x ⁹		x
Antibodies							
FVIII inhibitors ¹⁰	x	x			x	x	x
N8-GP binding antibodies ¹⁰	x	x			x		x
IgE, IgG and anti-HCP antibodies							x ¹¹
Biochemistry ¹²	x	x	x	x	x		x
Coagulation parameters ¹²							
aPTT	x ¹³	x	x	x	x		x
INR (PT)	x ¹³	x	x	x	x		x
FVIII activity ¹⁴							
FVIII trough level ¹²		x	x	x	x		x
FVIII recovery	x ¹⁵	x	x	x	x		x
Haematology ¹²	x	x	x	x	x		x
OTHER ASSESSMENTS							
PRO questionnaires	x ¹⁶						
HE assessments					x		
TRIAL MATERIAL							
Administration of trial product ¹⁷	x	x	x	x			x
IV/WRS call	x	x ⁵	x	x	x		x
Drug accountability		x ⁵	x	x	x		x

Visit number	1	2	3	4	5	Follow-up Visit	Un-scheduled Visit
Time of visit (Day)	Screening ¹	0 Surgery	1-6 ²	7-14 ²	EOT ³	Visit FU ⁴	
Visit window	0-3 w before Visit 2					4 w after EOT ±2 w	
Dispensing trial product	x ¹⁸	x ⁵	x	x			x
Dispensing trial card	x						
Dispensing/adjusting eDiaries	x						
REMINDERS/TRAINING							
Affirmation statement					x	x	
End of trial					x	x	
eDiary training	x	x	x	x			x
eDiary review		x ⁵	x	x	x		x
Home treatment training	x	x	x	x			x

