- The transfer to pathfinderTM 3 will be performed either on a scheduled or an Unscheduled Visit in pathfinderTM 2. Assessments performed in pathfinderTM 2 may be used as the Screening Visit assessments in pathfinderTM 3. All the assessments pertaining to the Screening Visit must have been done within maximum 4 weeks of the Day of Surgery and the results must be available for evaluation. These results from pathfinderTM 2 will then be used in pathfinderTM 3. Patients coming from the on-demand treatment arm in pathfinderTM 2 must have FVIII activity recovery level measured at the Screening Visit, see Section 8.1.1. All assessments at Visit 1 and 2 must be performed.
- Assessments must be done every day during Days 1-6 (Visit 3), once during Days 7-14 (Visit 4) and hereafter once every week until the post-operative control has finalised, as judged by the Investigator. If the late Post-operative Period is extended beyond Day 14, the Investigator/medically qualified person must perform a visit schedule with the patient once every week.
- The EOT Visit can not be performed earlier than Day 14. If the EOT Visit is performed at Day 14, Visit 4 and 5 may be joined and assessments pertaining to both visits must be performed once.
- FU Visit is only for patients who have developed inhibitors.
- To ease the work flow at site, it is allowed to perform the following Visit 2 assessments on the day just prior to the surgery, if necessary.
- Assessments will only be performed once in pathfinderTM 2 and these results will be used in pathfinderTM 3.
- Physical examination, Vital signs and Body measurements only to be assessed at Days 1 and 6.
- Physical examination only to be assessed once during Visit 4 (during Days 7-14).
- Only body weight will be measured.
- Antibody sampling is required to be made pre-dose and after minimum 96 hrs wash-out.
- Conditional assessments, must only be made if a patient experiences an unexpected allergic/anaphylactic reaction, see Section 8.3.6.3.
- Assessment should be made pre-dose, if dosed.
- Coagulation parameters are collected pre-dose and additionally post-dose (30 ± 10 min) at Visit 1.
- FVIII activity tests for central laboratory must be collected in accordance with Section 8.3.8.4. FVIII recovery activity must be measured 30 min ± 5 min post-dose. Additionally all FVIII activity test results from the local laboratory must be recorded in the eCRF, see Section 8.3.7.2.

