8.1.3 Visit 3 to Visit 4 - Post-operative Period

The Post-operative Period consists of Day 1 to Day 14. The following assessments must be performed daily during Visit 3 (Days 1-6) and once during Visit 4 (Days 7-14). The EOT Visit cannot be scheduled earlier than Day 14.

Before the EOT Visit and re-entering the pathfinder™ 2 trial the patient should be judged by the Investigator to be ready to continue either the prophylactic or on-demand treatment as previously decided upon in the pathfinder™ 2 trial. If not, the Post-operative Period must be extended as judged by the Investigator beyond Day 14 and the Investigator/medically qualified person must perform this visit schedule with the patient once every week.

When the patient is discharged from the hospital, the patient must record bleeding episodes, dosing of N8-GP etc., in the eDiary (refer to Section [8.4.7](#) for details).

During the Post-operative Period it is recommended to administer N8-GP according to Section [5.4.1](#).

The samples taken 30 min (\pm 5 or 10 min) post-dose should not be taken from the same vein as previously used for administration of N8-GP.

In the Post-operative Period (Visit 3 and 4) the following assessments will be performed and/or recorded in the eCRF:

- Withdrawal criteria, see Section [6.5](#)
- Adverse events, see Section [12.1](#)
- Concomitant medication, see Section [11](#)
- Surgical Interventions, see Section [8.2.1](#)
 - Clinical evaluation of haemostatic response, see Section [8.2.1.1](#) and [8.2.2.2](#)
 - Consumption of N8-GP, see Section [8.2.1.2](#)
 - Blood product transfusions, see Section [8.2.1.3](#)
 - Evaluation of wound haematoma, see Section [8.2.1.4](#)
 - Drain volume, see Section [8.2.1.5](#)
- Bleeding episodes and/or eDiary review and rating severity of bleeding episodes, see Section [8.2.2](#) and [8.4.7](#)
- Physical examination, see Section [8.3.3](#)
- Vital signs, see Section [8.3.4](#)
- Body measurements (weight only), see Section [8.3.5](#)
- Infusions, see Section [8.4.6](#)
- Administration of trial product, see Section [8.5.1](#)

Blood sampling for local laboratory assessments:

- Haemoglobin, see Section [8.2.1.6](#)
- FVIII activity, see Section [8.3.7.2](#)
- Haematology, see Section [8.3.7.3](#)

Blood sampling for central laboratory assessments:

- Biochemistry, see Section [8.3.8.2](#)
- Coagulation parameters, see Section [8.3.8.3](#)
- FVIII activity, see Section [8.3.8.4](#)

Trial material, training and reminders

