8.2.2.2 Definition of Haemostatic Response

- **Excellent:** abrupt pain relief and/or unequivocal improvement in objective signs of bleeding within approximately 8 hrs after a single infusion
- **Good:** definite pain relief and/or improvement in signs of bleeding within approximately 8 hrs after one infusion, but possibly requiring more than one infusion for complete resolution
- **Moderate:** probable or slight beneficial effect within approximately 8 hrs after the first infusion; usually requiring more than one infusion
- **None:** no improvement, or worsening of symptoms

The assessment for haemostatic response will be made by the patient or patient's caregiver and discussed with the Investigator during visits to the site.

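### Post-operative haemostatic effect is rated by treated-bleed definitions, so a surgery without a bleed has no category and the two summaries would most plausibly cover only surgeries that bled

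*Combined protocol and SAP*

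**What the plan says.** The Summary (Section 1) lists as a key secondary endpoint "Haemostatic effect of N8-GP during the post-operative period Days 1-6 and 7-14". Sections 4.2.2.1 and 18.2.4.2 list the two periods as separate endpoints. None of these places adds a condition that the patient must have bled. Section 18.2.4.2 plans only summaries and listings.

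Section 8.2.1.1 defines a four-point scale for the operation itself, anchored on what is expected for the type of procedure. For the post-operative period it changes scale: "Clinical evaluation of haemostatic response during the Post-operative Period, Days 1-6 and 7-14 will be assessed by the definitions described in section" 8.2.2.2. That section belongs to the part of the protocol on bleeding episodes. Its top level is "abrupt pain relief and/or unequivocal improvement in objective signs of bleeding within approximately 8 hrs after a single infusion" and its bottom level is "no improvement, or worsening of symptoms". It adds: "The assessment for haemostatic response will be made by the patient or" the caregiver, with discussion with the investigator at site visits.

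In Table 2-1 the row "Clinical evaluation of haemostatic response" is marked at Visits 2, 3 and 4 with no footnote limiting it to patients who bleed. Bleeding episodes have their own row. Table 2-2 marks the evaluation at Day 1. Section 8.1.3 introduces its list, which includes this item, with "The following assessments must be performed daily during Visit 3 (Days 1-6) and once during Visit 4 (Days 7-14").

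Section 5.4 describes N8-GP before, during and after major surgery as preventive treatment.

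**The concern.** The scale answers how well an infusion treated a bleed. The objective in Section 4.1.2 asks how well haemostasis held in the post-operative period. The two coincide only in patients who bleed.

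A patient whose haemostasis holds has no bleeding signs to improve and no treating infusion from which to count about 8 hours. The best outcome therefore cannot be scored. If such surgeries are left out, the summary is conditional on a post-operative bleed, which is itself an unfavourable event. A product that prevented nearly every bleed would then be described by its few worst cases.

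Two smaller gaps follow from the same cross-reference. The named assessor in 8.2.2.2 is the patient or caregiver, whereas 8.1.3 lists the item as a site assessment. And no visible text says how repeated ratings in Days 1-6 become one value.

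**Working it through.** The plan states no figure on this point. Section 18.1 takes the sample size from a guideline, so there is nothing to reproduce. The check is mainly a reading of the sections against each other.

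**1. Can a bleed-free patient be placed on the scale?** In 8.2.2.2, *Excellent* and *Good* need pain relief or improvement in signs of bleeding after infusion. *Moderate* needs at least a slight benefit after a first infusion. *None* needs symptoms that failed to improve or got worse. Every level presupposes symptoms, so none applies.

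**2. Is the evaluation meant only for bleeds?** The endpoints, Table 2-1, Table 2-2 and Section 8.1.3 carry no such condition. Section 8.2.2 already collects an effect rating for each bleeding episode. On a bleeds-only reading, the scheduled evaluation would repeat that item.

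**3. What would a site enter?** Section 13.1 says irrelevant CRF questions are to be marked according to the data entry instructions and gives not applicable as the example. This is the most plausible entry for a bleed-free patient. Section 18.2.4.2 does not say how such entries enter the summary.

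**4. Did an amendment change it?** The displayed changes leading to version 2 go from 8.1.1 to 8.3.5. Those leading to version 3.0 go from 8.1.5 to 8.2.2 and then stop. Those in Amendment 5 go from 8.1.5 to 8.3.6.1. None displayed touches 8.2.1.1. Because the version 3.0 text is incomplete, its wording of 8.2.2.2 cannot be fully confirmed.

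**5. Counts.** Section 5.1 plans at least 15 major surgeries.
- Endpoint values: 15 × 2 periods = 30.
- Scheduled ratings, upper bound if the evaluation is daily in Days 1-6: 15 × (6 + 1) = 105.

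**6. Illustration of the rated fraction.** The documents give no post-operative bleed rate, so *q* is assumed. Expected ratable surgeries = 15*q*. The last column is the exact binomial probability, treating surgeries as independent.

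| Assumed *q* | Ratable | Not ratable | P(at least 5 ratable) |
|---|---|---|---|
| 10% | 1.5 | 13.5 | 0.013 |
| 20% | 3.0 | 12.0 | 0.164 |
| 30% | 4.5 | 10.5 | 0.485 |
| 50% | 7.5 | 7.5 | 0.941 |

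**7. Illustration of the denominator.** Assume *b* of 15 surgeries bleed, one of those bleeds responds poorly and the rest respond well. The share with a favourable result is:

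| *b* | Bleed-free not applicable: (*b* − 1)/*b* | Bleed-free counted as favourable: 14/15 |
|---|---|---|
| 2 | 1/2 = 50% | 93% |
| 3 | 2/3 = 67% | 93% |
| 7 | 6/7 = 86% | 93% |

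The post-operative course has one failure in 15 in every row. Only the denominator changes.

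**The case against.** The strongest reply is that treated bleeds are what the plan means. The definitions sit under bleeding episodes, 8.1.3 points to them expressly, and Section 5.2 justifies the post-operative endpoints by the risk of re-bleeding. A mark in the flow chart need not mean a value for every patient: transfusions are marked too, and are recorded only when given. This reading is tenable. It does not remove the problem, because no text states the restriction or the denominator, and an endpoint so restricted does not answer the objective over all surgeries.

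It is also fair that the consequence is limited. Section 18.2.3 names no confirmatory secondary endpoints. Bleeding episodes in Days 1-14 must be recorded (Section 8.2.2), so bleed-free surgeries can be counted. Narratives, haematoma, drain and transfusion data remain. All of this stands. A lighter remedy, stating the denominator and that count, would make the summary honest but still leave most good outcomes unrated.

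A reader might infer that bleed-free patients fall into *None*, since nothing improved. With 3 bleeders and one failure that would give 2/15 = 13%. The documents do not support this as the likely result: the level presupposes symptoms, and Section 13.1 offers a not-applicable route.

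A reader might also take 105 ratings as a firm requirement. Section 8.2.1.1 names only the two periods, while 8.2.1.4 and 8.2.1.5 say daily for their own items, so 105 is an upper bound. Likewise, 8.2.2.2 does not leave the patient alone with the rating: the investigator discusses it, and in hospital bleeds are recorded by the investigator or qualified staff.

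**Conclusion.** The concern holds in this form: the post-operative rating uses a scale on which a bleed-free surgery has no place, and the most plausible result is two key secondary summaries restricted to surgeries that bled, with no stated denominator. It should be fixed because a suitable scale already exists in the same section.

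The size cannot be computed from the documents. At an assumed bleed rate of 10% to 50%, half to nine tenths of surgeries would be unrated (7.5 to 13.5 of 15). The percentages in the denominator table are illustration only.

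A reader might go further and conclude that the trial's efficacy evidence is undermined. The documents do not support that: the primary endpoint has its own scale and the post-operative endpoints are descriptive. The conclusion also assumes that version 3.0 left 8.2.2.2 unchanged and that no eCRF instruction or separate analysis text, neither of which is visible, supplies the missing rule. Confidence is therefore moderate.

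**What to change.** Amend Section 8.2.1.1 so that:

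- The investigator or surgeon rates every surgery once per post-operative period on the expectation-based four-point scale already in that section.
- Days 1-6 are rated at the Day 6 assessment. Days 7-14 are rated at the last Visit 4 assessment, or at the joined Visit 4 and EOT Visit. Each rating states the days it covers.
- The scale's wording on change of treatment regimen is adapted so that post-operative dose adjustment already allowed by Section 5.4.1 does not by itself decide the category. This wording separates *Moderate* from *None* and must be agreed before use.

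In Section 18.2.4.2, summarise over all surgeries and show the number not rated. Keep 8.2.2.2 for individual treated bleeds, reported separately with the number of surgeries that had any post-operative bleed.

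The cost is protocol wording and one eCRF item per period at assessments already scheduled: 30 ratings for 15 surgeries, against up to 105 if the present schedule is read as daily. No reduction rule is then needed. The rating remains subjective, open-label and partly recalled. If Visit 4 is held early, later events in Days 7-14 will appear only in the bleeding records.
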